It remains unknown which behavior change techniques are needed to optimize intervention effectiveness, a critical step to understanding mechanisms of change and informing next-generation text message alcohol interventions [13]. Our group's alcohol text message intervention [11], which was informed by self-regulation theories [14] and the Theory of Planned Behavior [15], used two behavioral change techniques with the largest effect sizes in a meta-analysis of alcohol interventions [16]: self-monitoring and goal commitment, in addition to feedback on drinking behavior, to reduce young adult hazardous drinking. To examine which combination of behavioral change techniques was driving reductions in young adult hazardous drinking, we deconstructed our combined behavioral change techniques intervention (i.e. COMBO) into the following interventions: (1) TRACK (self-monitoring of drinking intentions, desire to get drunk and alcohol consumption) [17]; (2) PLAN (feedback on drinking intentions and desire to get drunk) [18]; (3) USE (feedback on drinking quantity consumed) [19]; and (4) GOAL (prompts to set a personal goal to limit drinking, tips to achieve the goal and feedback on goal success) [20].

Study Objectives

This study used a randomized controlled trial (RCT) design to examine the effects of PLAN, USE, GOAL and COMBO relative to an assessment control arm (i.e. TRACK) on reducing alcohol consumption at 3- and 6-month post-randomization among young adults with hazardous drinking in the emergency department (ED). The primary hypothesis, based on our prior studies [11, 22], was that there would be an ordered effect of the intervention in reducing the number of binge drinking days at 3-month post-randomization. That is, compared with the TRACK, (1) the combination of behavioral change techniques (i.e. COMBO) would show the greatest reductions in past month binge drinking days at 3-month follow-up and (2) component behavioral change

techniques (i.e. PLAN, USE and GOAL) would show intermediate reductions in past month binge drinking days at 3-month follow-up. We did not compare the four active conditions against each other. We explored intervention effects on secondary outcomes of binge drinking prevalence, drinks per drinking day and past month number of negative drinking consequences at 3- and 6-month follow-ups.

Study Design & Methods

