For intent-to-treat (ITT) analyses, following current recommendations when outcomes are missing [41, 42] and following best practices for alcohol trials [43], we used multiple imputation procedures to generate accurate estimates of uncertainty. We first ensured that missing outcome data were not missing completely at random (MCAR) using Little's test [44]. We therefore assumed that outcomes were missing at random (MAR) [45]. To reduce probability of

outcomes being missing due to unmeasured factors (i.e. missing not at random: MNAR), we examined baseline covariates associated with missing outcomes (see Supporting information, Table [S3](#)) and included those with significant associations in the imputation model. Because the pattern of missingness was non-monotonic, we used multiple imputation chained equations (MICE) [\[46\]](#). Because missing binge drinking days were not normally distributed and bounded by 0 to 30 day, we used predictive mean matching with $k = 5$ nearest neighbors [\[47\]](#). We included sex, college-enrolled, tobacco use and baseline impulsivity score as predictors of outcomes. We generated 30 sets of imputed data based on the highest fraction of missing information, which was 0.27, as per recommendations [\[48\]](#). We checked how well the imputation model fitted the observed outcome data by inspecting their distributions in each treatment arm.

Analytical models

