For our primary outcome analysis of mean binge drinking days at 3-month follow-up as well as the secondary outcome analysis of mean binge drinking days at 6-month follow-up, we used separate negative binomial regression functions [\[49\]](#). Secondary outcome analyses also included at 3- and 6-month mean drinks per drinking day using the Poisson regression function, the point prevalence of any binge drinking days in the past month using the logit function and mean number of negative alcohol consequences (B-YAACQ) using a negative binomial regression. Covariates with significant univariate associations with the primary and secondary outcomes were included in the models as covariates, and white race, baseline tobacco use, baseline impulsivity score and baseline measures of the main outcome (e.g. binge drinking days) were kept in the final models, as their inclusion improved model fits (based on Akaike information criterion and Bayes information criterion). Interactions between intervention arm and site of recruitment were examined, and no significant interactions were identified in relation to the primary or secondary outcomes. Estimated treatment effects are reported as either adjusted β or odds ratios (ORs) with 95% CIs. Sensitivity of all imputed model findings was assessed by conducting complete case analyses (CCA).

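### The documented imputation predictors leave out randomised arm; if the list is complete and missingness is similar across arms, contrasts with TRACK shrink by roughly 8–30%

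*Combined protocol and SAP*

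**What the plan says.** Under Statistical Considerations, the section on missing outcomes makes multiple imputation the basis of the main analysis: "For intent-to-treat (ITT) analyses, following current recommendations when outcomes are missing", the trial used multiple imputation. It assumes that data are missing at random and uses chained equations because missingness is non-monotonic. Binge-day counts are imputed by predictive mean matching with five donors.

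Baseline covariates were screened for association with missing outcomes, and the authors "included those with significant associations in the imputation model". The predictors follow: "We included sex, college-enrolled, tobacco use and baseline impulsivity score as predictors of outcomes". On the number of imputations: "We generated 30 sets of imputed data based on the highest fraction of missing information, which was 0.27". Arm appears in this section only at the end, where the distributions are inspected by arm as a check on fit.

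The Analytical models section fits negative binomial regressions for binge days and keeps in the final models "white race, baseline tobacco use, baseline impulsivity score and baseline measures of the main outcome". Complete case analysis is the stated sensitivity analysis.

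Study Objectives sets the contrasts. Each active arm is compared with TRACK at 3 months; "the combination of behavioral change techniques (i.e. COMBO) would show the greatest reductions in past month binge drinking days", and PLAN, USE and GOAL are expected to show intermediate effects.

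**The concern.** An imputation model should contain at least the variables whose relation to the outcome the analysis model estimates. Here the key variable is arm, and the text does not place it in the imputation. The selection rule would not be expected to bring it in either: arm is not a baseline covariate, and if missingness is similar across arms it would not be associated with missingness.

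Without arm, predictive mean matching draws donors from all five arms. Imputed values then carry no treatment effect, or only an indirect one through the other visit's outcome if that was in the chain. The use of chained equations for non-monotonic missingness suggests that it was, which is the milder case.

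This would not create a false benefit. It would hide real ones in the main analysis of the primary hypothesis, most seriously for the three component arms, where only intermediate effects are expected.

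**Working it through.** **Inputs from the document.** Four listed predictors; predictive mean matching with 5 donors; 30 imputations; highest fraction of missing information (FMI) 0.27; negative binomial analysis with arm, race, tobacco, impulsivity and baseline outcome; four contrasts with TRACK. Missing rate, sample size, effect sizes and between-visit correlation are not given.

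**Assumptions.** Rate ratios against TRACK of 0.70 (COMBO) and 0.85 (PLAN, USE, GOAL); equal allocation; missing fraction f equal across arms.

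**1. The plan's own figure.** The document does not state its rule for the number of imputations. Taking the common one, m ≥ 100 × FMI = 100 × 0.27 = 27, which 30 meets. Relative efficiency is 1/(1 + 0.27/30) = 0.991. The number of imputations is adequate; raising it would not remove a bias.

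**2. Closed form with pooled donors.** The completed mean in arm a is (1 − f)μ_a + f·μ̄, where μ̄ is the pooled mean. A difference from TRACK is therefore (1 − f)(μ_a − μ_TRACK), a loss of exactly f.

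On the log scale, set TRACK to 1, so μ̄ = (1 + 3 × 0.85 + 0.70)/5 = 0.85. At f = 0.20 the apparent COMBO rate ratio is (0.8 × 0.70 + 0.2 × 0.85)/(0.8 + 0.2 × 0.85) = 0.73/0.97 = 0.753. Then ln 0.753 / ln 0.70 = 0.284/0.357 = 0.797, a loss of 20.3%. The same formula gives 10.2% at f = 0.10 and 30.4% at f = 0.30.

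**3. Simulation with 150 per arm** (185 trials per rate; counts capped at 30; missingness driven by the four listed variables; 60% of participants with linked missing status at both visits). Share of the full-data COMBO log rate ratio kept (Monte Carlo SE 0.009–0.017):

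| Missing | Listed predictors, other visit not in chain | Listed, other visit in chain | Arm, baseline and race added | Complete case |
|---|---|---|---|---|
| 10% | 0.89 | 0.90 | 1.00 | 1.00 |
| 15% | 0.83 | 0.85 | 0.99–1.00 | 1.01 |
| 20% | 0.77 | 0.79 | 0.99–1.00 | 1.00 |
| 25% | 0.73 | 0.75 | 0.98–1.00 | 1.00 |

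**4. Further simulations.**
- With 3,000 per arm and listed predictors only, shrinkage across the four contrasts was 8–9% at 8% missing, 9–12% at 10%, 18–20% at 20% and 30–32% at 30%. With the 6-month outcome in the chain, mean shrinkage was about 7–8% at 10% missing and 11% at 15%; individual contrasts shrank by 13–19% at 20% and 17–26% at 30%.
- A 400-trial run at 10/15/20/27% missing kept 0.88/0.82/0.76/0.69 of the effect (not in chain) and 0.92/0.88/0.85/0.79 (in chain).
- One more run, not in chain, kept 0.90/0.82/0.78/0.70 at the same rates, against 0.97–1.01 with arm added.

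**5. Which omission matters.** In the 3,000-per-arm simulation, adding arm alone left −4% to +2% shrinkage at 20% and 30% missing, which is simulation noise. Adding baseline and race without arm left 16–21% and 28–31%. The shrinkage comes from arm; omitting baseline and race costs precision and agreement with the analysis model.

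**6. Link to FMI 0.27.** In the 150-per-arm design the mean highest FMI equals 0.27 at 9–17% missing, depending on which coefficients and visits are counted and whether the other visit is in the chain; shrinkage there is 10–18%. In a design with 180 per arm and listed predictors only, the highest mean FMI was 0.20 at 20% missing and 0.28 at 30%. With the 6-month outcome in the chain, that design was compatible with about 10–30% missing. The stated FMI therefore does not pin down the rate.

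**7. Power.** In the 150-per-arm design at 15% missing, COMBO power was 57–61% with the listed predictors, 77–79% with arm, baseline and race added, and 78% for complete cases (SE 0.03–0.04).

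**The case against.** The four variables may be only the outcome of the screen for predictors of missingness, with arm and the analysis covariates included by default. That two of them are also analysis covariates does not settle it, since tobacco use and impulsivity can predict both missingness and outcome. The other visit's outcome is not listed either, yet it was probably in the chain. Fit was inspected by arm, so arms were not wholly ignored, and the supporting table of missingness predictors is not available here. This stands as a limit on certainty: the text does not settle whether arm was used. Inspecting distributions by arm is a diagnostic, however, not a model term.

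The percentages rest on assumptions, and the designs above place an FMI of 0.27 at different missing rates. That also stands; 8–30% is a conditional range. The power comparison changes arm, baseline and race together, so the whole gap cannot be credited to arm. In one simulation arm alone recovered about half to all of the lost power.

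Finally, the error is conservative, and the complete case analysis would tend to expose it. True, but that analysis is only a sensitivity analysis and does not correct the main one.

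**Conclusion.** The concern holds. As documented, the imputation behind the main analysis does not include randomised arm, and followed as written it biases every contrast with TRACK towards no effect. The loss is about equal to the missing fraction, or somewhat less if the other visit's outcome was in the chain: roughly 8–30% of the log rate ratio over assumed missing rates of about 8–30%. More missing data would mean more shrinkage.

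This depends on the listed predictors being complete and on similar missingness across arms; with differential missingness the shrinkage would not be uniform. If arm was in fact included, the fault disappears and only the reporting needs correcting. It should be fixed; confidence is medium because the text leaves the full model unstated.

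**What to change.** State in the SAP the full imputation model, and say whether arm was in the chained equations or imputation was done within arm. The model should contain:

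- randomised arm (or be run by arm);
- the baseline value of each outcome;
- white race and the other analysis-model covariates;
- the present auxiliaries, sex and college enrolment;
- the outcomes at the other visit.

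Report the missing rate by arm and visit. If the imputations already run omitted arm, re-impute and repeat the intention-to-treat analyses; until then, read the complete case estimates alongside the imputed ones.

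The cost is a short addition to the text and, only if arm was left out, a re-run on data already collected.

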Secondary outcomes included number of binge drinking days at 6 months as well as drinks per drinking day and prevalence of any binge drinking at 3 and 6 months, all derived from the 30-day TLFB. We calculated drinks per drinking day as the mean drinks divided by the number of days with any alcohol consumption. We calculated the prevalence of any binge drinking days in the past 30 days, represented as a dichotomous variable (1 = any binge drinking day; 0 = no binge drinking day). Secondary outcomes also included alcohol-related consequences from the Brief Young Adult Alcohol Consequences Questionnaire (B-YAACQ) [40]. The B-YAACQ is a 24-item measure of alcohol-related problems that utilizes a dichotomous (present or absent) scoring format. Higher scores (count of items marked as 'present') on the B-YAACQ not only indicate a wider variety but also reflect a more severe pattern of alcohol-related problems.

Eligibility Criteria

Patients aged 18–25 years who presented to one of four EDs in western Pennsylvania were eligible to be screened if they were medically stable, provided permission to be approached and were not being discharged imminently. Patients were excluded from screening in the ED if they were already enrolled into the trial or were not interested in study participation. Screened patients were included if they reported an Alcohol Use Disorder Identification Test for Consumption (AUDIT-C) score of ≥ 3 for women or ≥ 4 for men [23]. We used the AUDIT-C to screen-in patients as it is a brief alcohol screening instrument that reliably identifies people who are hazardous drinkers or have active alcohol use disorders (including alcohol abuse or dependence) [24] and permits comparison to prior studies [11]. Screened patients were excluded if they reported not being interested in participating in a clinical trial, past treatment for drug or alcohol problems, current psychiatric treatment or did not own their own telephone with text messaging.

Statistical Considerations

Missing outcomes (primary and secondary)

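### Drinks per drinking day (secondary outcome) is a per-person average fitted by Poisson regression with no robust variance stated, so its 95% confidence intervals may be too wide or too narrow

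*Combined protocol and SAP*

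**What the plan says.** The Secondary outcomes section defines the variable: "We calculated drinks per drinking day as the mean drinks divided by the number of days with any alcohol consumption". It is measured at 3 and 6 months from the 30-day drinking calendar. Study Objectives treats it as exploratory: "We explored intervention effects on secondary outcomes of binge drinking prevalence, drinks per drinking day".

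The Analytical models section assigns the model: "mean drinks per drinking day using the Poisson regression function". It names no sandwich variance, scale parameter or dispersion check. In the same section, binge drinking days get negative binomial regression, and so do consequences: "mean number of negative alcohol consequences (B-YAACQ) using a negative binomial regression". On reporting, it says: "Estimated treatment effects are reported as either adjusted β or odds ratios (ORs) with 95% CIs".

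For missing outcomes, the plan uses multiple imputation: "We generated 30 sets of imputed data based on the highest fraction of missing information, which was 0.27". The sensitivity analysis for every imputed model is a complete case analysis.

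No section says how a participant with no drinking days in the 30-day window is handled.

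**The concern.** Poisson regression takes its default standard errors from the assumption that, given the covariates, the variance equals the mean. That can be reasonable for a count of independent events. It has no basis for an average over a number of days that differs between participants. The spread of such an average depends on how much people differ from one another and on how many days each average covers, and nothing ties it to the mean.

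The negative binomial models for the two count outcomes can absorb spread above the Poisson value. No allowance in either direction is stated for this outcome. If the residual spread is below the Poisson value, the intervals are too wide and real effects may be missed. If it is above, the intervals are too narrow and chance differences may be reported as effects.

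The planned safeguards do not cover this. Multiple imputation dilutes the error, because the between-imputation part of the variance does not come from the Poisson formula. The complete case analysis lacks even that dilution.

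**Working it through.** The plan gives no mean, SD, arm size or share of non-drinkers for this outcome, so it has no figure to reproduce. The check asks how far the default interval can be off.

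**Inputs**
- Nominal level 95%, critical value 1.96 (interval level from Analytical models).
- Fraction of missing information f = 0.27 (Missing outcomes section). This is the highest value stated there and is not tied to this outcome. The complete case analysis has f = 0.
- Assumed: mean 4; SD 1.5, 2, 2.5 or 3; correlation r = 0.5 between baseline and outcome. The plan keeps baseline measures of the main outcome in the final models, so an adjusted calculation is the relevant one.

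**Formulas**
- Residual variance relative to the Poisson value: φ = SD² × (1 − r²) / mean.
- With the correct model, the within-imputation variance is a share (1 − f) of the total. The Poisson formula replaces it by (1 − f)/φ and leaves the between-imputation share f unchanged. So Poisson width / correct width = √[(1 − f)/φ + f].
- True size of a nominal 5% test = 2 × [1 − Φ(1.96 × width ratio)].

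**Worked case, SD 3:** φ = 9 × 0.75 / 4 = 1.6875. With f = 0.27, 0.73/1.6875 + 0.27 = 0.7026, and its square root is 0.84. The size is 2 × [1 − Φ(1.643)] = 10.0%.

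| SD (assumed) | φ | Width ratio, f = 0.27 | Size, f = 0.27 | Width ratio, complete cases | Size, complete cases |
|---|---|---|---|---|---|
| 1.5 | 0.42 | 1.41 | 0.6% | 1.54 | 0.25% |
| 2 | 0.75 | 1.12 | 2.9% | 1.15 | 2.4% |
| 2.5 | 1.17 | 0.945 | 6.4% | 0.92 | 7.0% |
| 3 | 1.69 | 0.84 | 10.0% | 0.77 | 13.1% |

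The sign changes at φ = 1, which is SD = √(4/0.75) = 2.31 under these assumptions.

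**Does the remedy work?** A simplified simulation (two arms of 150, gamma outcome, one baseline covariate with r = 0.5, 27% missing, predictive mean matching, 30 imputations) used the same four SDs. With sandwich errors the size was 4.8% to 5.7% with imputation and 5.2% to 5.5% in complete cases. The default Poisson sizes were 0.6% to 10.0% and 0.2% to 13.0%, in line with the closed form. This is not a replica of the five-arm analysis, and its imputation set-up is assumed.

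**No drinking days.** The quotient is then 0/0, and the rule chosen moves the estimate itself. Suppose drinkers in two arms drink equally per occasion, and the arms have 10% and 20% abstainers (assumed). Scoring abstainers 0 gives 0.80/0.90 = 0.89. Restricting to drinkers gives 1.00. Zeros also add spread: with mean 4 and SD 2 among drinkers, the unadjusted variance/mean is SD²/mean + p × mean. That is 1.0 with no abstainers, 1.4 at p = 10% and 1.8 at p = 20%.

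**Numerator.** Read literally, the definition divides a mean by a number of days. For 60 drinks on 10 drinking days, the intended value is presumably 60/10 = 6.0. The literal wording gives 6/10 = 0.6 (mean per drinking day) or 2/10 = 0.2 (mean per calendar day).

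**The case against.** **Silence is not error.** The text is a short methods account that gives no standard-error method for any model, so sandwich errors may have been used. This stands as a limit: a reader might infer that a faulty analysis was run, and the documents do not show that. They show a method which, followed as written, gives unreliable intervals, and a better one costs a single option.

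**A non-integer outcome does not invalidate Poisson regression.** This is correct. A reader might infer that the estimated effects are biased. They are not on this ground, because the mean ratio is consistent if the mean model is right. Only the variance is in question.

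**The size rests on assumptions.** This is also correct. At SD 2 to 2.5 with imputation, the size is 2.9% to 6.4% and the width ratio 1.12 to 0.945, which is close to nominal. A reader might take the outer values as the trial's error rates, or assume that the intervals are too narrow. The documents support neither.

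**Drinks per drinking day is naturally conditional on drinking.** This is a fair position. Scoring abstainers 0 gives a composite of abstaining and intensity, and abstinence already counts as zero binge days in other outcomes. The documents do not make scoring 0 the only right answer. What is missing is a stated rule.

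**The numerator is a wording slip.** Very probably. Nothing shows that the variable was computed wrongly.

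**Conclusion.** The concern holds for the variance of one model. As written, the 95% intervals for drinks per drinking day rest on variance equal to mean, with no basis given for that. The direction and size of the error cannot be known from the documents. Under the assumed values, the intervals range from 41% too wide to 16% too narrow with imputation. The complete case analysis is somewhat more exposed, with test sizes of 0.25% to 13.1%. These figures depend on the assumed mean, SD and correlation, and on applying 0.27 to this outcome.

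The missing rule for participants with no drinking days is a separate gap in the definition. It decides who is analysed and moves the point estimate, so it is more than a matter of interval width. The numerator needs only a clearer sentence.

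A reader might extend the doubt to the trial's main result. That is not supported: the primary outcome is binge drinking days at 3 months, with a negative binomial model.

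**What to change.** 1. **Variance.** Keep the log-link model. State and use sandwich standard errors within each of the 30 imputed data sets before pooling, and in the complete case analysis. If they were already used, one sentence saying so closes this part. Negative binomial regression is not an equivalent remedy, because it cannot represent spread below the Poisson value.
2. **Numerator.** State that the outcome is total standard drinks in the 30-day calendar divided by days with any drinking, and check the derived variable against the calendar data.
3. **No drinking days.** State the rule. Participants observed to have abstained should not be treated as missing and imputed as drinkers. Whether they are scored 0 or the analysis is limited to drinkers is an estimand choice for the sponsor to declare. A drinkers-only result should be labelled as conditional on a post-randomisation outcome, and so not a fully randomised comparison. For example, if an arm's only effect were that its lightest 10% of drinkers stopped (gamma outcome, mean 4, SD 2 or 2.5 assumed), the drinkers-only ratio would be 1.07 or 1.09, an apparent harm.

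The cost is a few sentences, one model option, a re-run of this outcome and one derivation check, with no new data. The downside is that sandwich errors can let test size rise slightly above 5% in small samples: up to about 6% in complete cases in the simplified simulation with 150 per arm, where that maximum came with a baseline unrelated to the outcome.

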The study was a parallel five-group individually randomized clinical trial that compared the efficacy of 12-week interventions utilizing different behavioral change techniques on reducing binge drinking at 3- and 6-month post-randomization among young adults with hazardous drinking. Assessor-blinded self-reported outcomes at 3 and 6 months were examined. The study was funded by the National Institute on Alcohol Abuse and Alcoholism (NIAAA). The study protocol was approved by the University of Pittsburgh Human Research Protection Office.

Participants who completed the baseline assessment were instructed to text a study telephone number within 24 hours. Only individuals whose telephone numbers matched the telephone numbers provided during the enrollment process were eligible. Once this match was recognized, participants received several texts welcoming them to the study and describing the 2-week run-in prior to randomization. During the 2-week run-in following the ED enrollment, on the 2 days in the week when participants typically drank alcohol (based on self-report data collected at baseline), subjects were prompted at 3 p.m. to report drinking plans and desire to get drunk, without receiving any directive feedback. This design feature of delivering messages on days when subjects typically drank was intended to ensure that we efficiently captured reports of drinking on days when it typically occurred. If no response was received within 2 hours, each text query was repeated once, and the response window closed after an additional 2 hours if no response was received. Only individuals who responded to at least 50% of the text queries and responded that they wished to continue participation with 'GO' at the end of the 2-week run-in were randomized to one of the five conditions. Randomization was performed by the software sequentially selecting a condition assignment in blocks of 10 from a randomization list generated a priori and concealed from participants and research staff throughout the trial.

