The interventions were all delivered via an automated text messaging intervention for 12 weeks using software run by the Office of Academic Computing at the University of Pittsburgh Medical Center. We chose text messaging, given its ubiquity and preferential role for communication among young adults [17] as well as its proven effectiveness to deliver other health support [18]. Each intervention arm was designed to focus upon a unique component or combination of behavioral change techniques, as shown in Supporting information, Table S1 and as described in prior work [3]. The TRACK arm was intended to promote self-monitoring [17] of plans to drink, desire to get drunk and alcohol consumption and was identical to the run-in messaging. The PLAN arm was intended to challenge drinking expectancies [18] by providing feedback on drinking plans and desire to get drunk in addition to promoting self-monitoring. The USE arm was intended to modify post-drinking appraisals [19] by providing feedback on reported number of drinks consumed after their typical drinking day. The GOAL arm provided self-regulation support to limit alcohol consumption [20] by prompting drinking limit goal commitment [25], providing feedback on goal self-efficacy [26] and providing feedback on goal success to either bolster future goal striving [27] or reframe goal failure [28]. The COMBO arm combined all of the above behavioral change techniques [3].

Primary outcome

The primary outcome was the number of past month binge drinking days at 3-months post-randomization calculated from a 30-day time-line follow-back (TLFB) calendar [39]. Participants completed a web-based calendar and a visual reference displaying standard drink amounts and were asked to report their alcohol consumption by day. A standard drink was defined as 12 oz. of beer, 5 oz. of 12% table wine, 12 oz. of wine cooler or 1.25 oz. of 80-proof liquor. We calculated the number of days when a woman reported four or more standard drinks or a man reported five or more standard drinks as a binge drinking day.

Secondary outcomes

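### The drinking covariate named in the models predates randomisation by about 2 weeks or more, and no newer run-in report is named; the comparison stays valid, but a little precision is probably lost

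*Combined protocol and SAP*

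**What the plan says.** **Order of events (Study Design & Methods).** The baseline assessment comes first: "Participants who completed the baseline assessment were instructed to text a study telephone number within 24 hours". Welcome texts follow, "describing the 2-week run-in prior to randomization". Randomisation comes after the run-in, and the 3- and 6-month outcomes are counted from randomisation.

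**What the run-in collects (same section).** Prompts went out "on the 2 days in the week when participants typically drank alcohol", and "subjects were prompted at 3 p.m. to report drinking plans and desire to get drunk, without receiving any directive feedback". That sentence mentions no drinking quantity. The stated reason for choosing those days, however, is that this was "intended to ensure that we efficiently captured reports of drinking on days when it typically occurred". The later description of the TRACK arm says that it covers "plans to drink, desire to get drunk and alcohol consumption and was identical to the run-in messaging".

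**How the run-in is used.** To be randomised, a person had to answer at least half of the queries and reply GO. No other use is described.

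**Covariates (Analytical models).** White race, tobacco use and impulsivity are named, and "baseline measures of the main outcome (e.g. binge drinking days) were kept in the final models". Covariates entered through univariate significance; the list of candidates is not given.

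**Imputation (Missing outcomes).** The named predictors are sex, college enrolment, tobacco use and impulsivity. The highest fraction of missing information is given as 0.27.

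**The concern.** Between the baseline assessment and randomisation, every participant has an ED visit and 2 weeks of messaging. The protocol equates that messaging with TRACK, which it presents as a self-monitoring technique. On the protocol's own reasoning, drinking could change over that interval, and more in some people than in others. Two people with the same enrolment count may therefore be in different states when randomised. If the run-in reports reflect that difference, leaving them out keeps it in the residual variation of the 3-month binge-day count and makes the contrasts with TRACK slightly less precise.

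The reports precede allocation, so adjusting for them cannot introduce post-treatment bias. Everyone randomised passed the response rule, so at least some run-in data exist for each person. The share of queries answered also measures engagement before randomisation, which makes it a natural candidate predictor of missing follow-up in an imputation model that assumes data are missing at random.

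**Working it through.** The documents give no sample size, power, standard deviation or covariate-outcome correlation, so there is no plan figure to reproduce. Every correlation below is an assumption.

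**1. Timing and amount of data.** The sequence is baseline, text-in within 24 hours, 2 weeks of run-in, randomisation. Prompted days: 2 per week × 2 weeks = 4 at most. With half the queries answered, the minimum is roughly 2 days' worth. The baseline measure covers 30 days if it uses the same calendar as the outcome (assumption).

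**2. Linear approximation.** Let B be the baseline count, R the run-in summary and Y the 3-month count.

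- R²(B) = rBY²
- R²(B,R) = (rBY² + rRY² − 2·rBY·rRY·rBR) / (1 − rBR²)
- Variance ratio = (1 − R²(B,R)) / (1 − R²(B)); the standard error (SE) scales with its square root and the effective sample size with its inverse.

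| rBY | rRY | rBR | R²(B,R) | Variance ratio | SE | Effective n |
|---|---|---|---|---|---|---|
| 0.4 | 0.2 | 0.5 | 0.12/0.75 = 0.160 | 0.840/0.840 = 1.000 | 0% | 0% |
| 0.5 | 0.4 | 0.5 | 0.21/0.75 = 0.280 | 0.720/0.750 = 0.960 | −2.0% | +4.2% |
| 0.4 | 0.5 | 0.3 | 0.29/0.91 = 0.319 | 0.681/0.840 = 0.811 | −9.9% | +23.3% |

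Over rBY 0.4-0.7, rRY 0.2-0.5 and rBR 0.3-0.7, the SE falls by between 0% and about 10%. This leaves out combinations with rRY < rBY·rBR, where a higher run-in value would have to predict fewer binge days at a given baseline. Reductions above 9% occur only with rRY = 0.5 and rBR = 0.3: a summary of at most 4 days that predicts the outcome well while being only weakly related to the same person's baseline drinking. That is a favourable corner.

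**3. Negative binomial simulation.** This used 400 patients in two arms and 60 replicates per setting, with log(1 + baseline binge days) in the model, with and without a run-in summary from 2 to 4 answered days.

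| Run-in content | Variance ratio | SE reduction | Effective n |
|---|---|---|---|
| Consumption | 0.96 to 0.90 | 1 − √0.96 = 2.0% to 1 − √0.90 = 5.1% | 1/0.96 = +4% to 1/0.90 = +11% |
| Plans and desire only (noisy proxy) | 0.985 to 0.955 | 1 − √0.985 = 0.8% to 1 − √0.955 = 2.3% | 1/0.985 = +1.5% to 1/0.955 = +5% |

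In one plans-and-desire setting the SE was 0.1102 unadjusted, 0.1035 with baseline and 0.1012 with baseline and run-in. Most of the gain comes from the baseline count that the plan already uses.

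Cross-check: the observed correlations in that setting were rBY 0.36, rRY 0.28 and rBR 0.27. The formula gives R²(B,R) = (0.1296 + 0.0784 − 0.0544)/0.9271 = 0.166 and a variance ratio of 0.834/0.870 = 0.959, close to the simulated 0.955.

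**4. Effect on power.** Starting from an assumed 80%, power = Φ((z₀.₉₇₅ + z₀.₈)/√ratio − z₀.₉₇₅). A ratio of 0.985 gives 80.6%, and 0.90 gives 84.0%.

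**5. Where this applies.** The argument concerns the negative binomial count models. In the logit model, adjustment changes the conditional odds ratio and the power rather than simply shrinking the SE. In the Poisson model, model-based SEs depend on fitted means and not on residual variance.

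**The case against.** The strongest reply is that this is an efficiency preference and not a defect. Allocation is randomised, the plan already adjusts for the baseline outcome, and the intervals are valid as they are. That stands. A reader might also infer that chance imbalance in run-in drinking biases the contrasts. It does not: randomisation and the confidence interval already allow for it, so this is the precision argument again.

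A reader might infer that the enrolment measure is the only drinking covariate and that run-in data were deliberately left out. The documents do not establish that. Covariates were screened univariately from an unlisted set, and run-in variables may have been tried and dropped. What can be said is that none is named. Nor did the run-in reports decide eligibility: response and the GO reply did, whatever the answers said.

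A partial correlation of 0.2 to 0.4 would give 1 − r² = 0.96 to 0.84, SEs 2.0% to 8.3% lower and 4% to 19% more effective participants. Nothing in the documents supports the upper end. The simulated variance ratios correspond to partial correlations of √0.015 = 0.12 to √0.10 = 0.32.

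Two practical objections also stand. The most useful variable, consumption, may not have been recorded, because the run-in and TRACK descriptions do not agree. And the 50% rule applies to all queries together. With two questions on each of 4 days (assumption), 4 of 8 answers suffice, and all 4 could be of one type, so an average for the other type can be undefined.

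**Conclusion.** The point holds as a modest efficiency improvement, not as an error of validity. It is firm that the named drinking covariate precedes randomisation by about 2 weeks or more, that newer pre-randomisation reports exist for everyone randomised, and that no run-in variable is named in either model.

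The size is not firm. Under the assumed correlations, event rates and sample size, the SE in the negative binomial models would fall by about 1-2% with plans and desire only, by about 2-5% with consumption, and by 0% if the run-in adds nothing beyond baseline. To say that free precision has been lost would go too far: the gain may be nil, and the added parameters are not free.

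**What to change.** 1. State what the run-in recorded, and reconcile its description with that of TRACK in Study Design & Methods.
2. In the negative binomial models, keep the baseline outcome and add two covariates fixed in advance rather than chosen by univariate screening: (a) one run-in summary, namely mean drinks per prompted day if consumption was queried, otherwise mean desire to get drunk over answered queries; and (b) the proportion of run-in queries answered.
3. Put both variables in the imputation model together with white race and the baseline outcome, which its named predictors omit. Without those two, adding run-in variables alone would still not align it with the analysis model. Impute the run-in summary there when no query of that type was answered.
4. Use no text report sent after randomisation.
5. The section is written in the past tense and reports findings. If outcomes have already been analysed, present this as a labelled sensitivity analysis, so that it does not become a further post hoc choice of covariates.

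Cost: two extra parameters, noisy summaries from at most 4 prompted days, a merge of the run-in text log with the analysis file, and a few sentences of text. No new data are needed.
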